8.5 Adjustment for Multiplicity

Adjustments for multiplicity will not be made in this early phase study.

9. Disposition of Subjects

Disposition will be presented in terms of numbers and percentage of subjects by dose group and for all subjects. Percentages will be calculated using treated subjects as the denominator unless otherwise specified.

The number of subjects who screened, screen failed, enrolled, and treated will be presented.

The number and percentages of subjects in each analysis set (Safety, Full, and Evaluable) will be presented.

The number and percentages of subjects who completed the study or discontinued from the study will be presented. The reasons for study discontinuation will include AE, death, lost to follow-up, physician decision, protocol violation, study terminated by sponsor, withdrawal of consent, and other.

The number and percentages of subjects with any protocol deviation, major deviation, and minor deviation will be presented. Major and Minor deviations will be further classified into the following sub-categories : informed consent, inclusion/exclusion or treatment assignment, test article/study drug infusion and assignment at site, improper protocol procedures at site (missed, repeated, not per protocol), site's failure to report serious SAE/AE, visit out of window (missed), visit out of window (early, late), subject's use of prohibited concomitant medication, subject's failure to follow instructions, investigator documented review and/or signature missing, inadequate source documents, other, and COVID-19 related. The percentages for each sub-category of major or minor deviation category will be based on the total number of subjects with major or minor deviations.

Subject listings including subject disposition, inclusion/exclusion criteria, and protocol deviations, will be provided.

10. Demographics and Baseline Characteristics

The demographic variables including age, sex, ethnicity, race, and female subjects' childbearing potential will be summarized using Safety Analysis Set.

Age (years) will be summarized by dose group and for all subjects using continuous descriptive statistics. In addition, age will be categorized into two age groups, <65 and ≥65, and summarized using counts and percentages.

Sex, race, and ethnicity will be summarized by dose group and all subjects using discrete descriptive statistics. Subjects who record more than one race will be grouped into a single category denoted as Multiple. Female childbearing potential will be summarized by counts and percentages based on the number of females in each dose group.

Other baseline characteristics, including weight and body mass index (BMI) at the Screening visit; ALSFRS-R total score at the Screening Visit and at baseline; dyspnea, orthopnea, and respiratory insufficiency ALSFRS-R sub-scores at the Screening visit and at baseline; time since ALS symptom onset (days); and time since ALS diagnosis (days), will be summarized by dose group and for all subjects using continuous descriptive statistics.

A subject listing for demographic variables along with weight and BMI at the Screening visit will be provided. Additionally, separate subject listings for ALS diagnosis at Screening and pregnancy test results for female subjects with childbearing potential will be provided.

11. Medical History and Concomitant Medications

11.1 Medical History

Medical history will be coded using Medical Dictionary for Regulatory Activities (MedDRA) Version 23.1. Medical history will be summarized using discrete summary statistics by dose group by system organ class (SOC) and preferred term (PT) using the Safety Analysis Set. Percentages will be based on the number of subjects in each dose group. If a subject reports the same PT multiple times within the same SOC, that PT will only be reported once within that SOC. As with the PT, if a subject reports multiple conditions within the same SOC, that SOC will only be reported once. In the summaries, SOCs and PTs within an SOC are listed in alphabetical order. On study procedures or surgeries will be coded using MedDRA 23.1 and reported with medical history.

A subject listing for medical history including procedure or surgeries will be provided.

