#### **6.2 Participant Screening**

The purpose of Screening Visit 1 is to thoroughly inform, both verbally and in writing, the potential participant about the study and allow him/her the opportunity to ask questions. The potential participant will then sign and date the informed consent form and screening procedures can be performed. Once the consent form is signed the participant is considered enrolled into the study and any serious adverse events that occur will be captured from the date of consent until the end of study participation.

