### 6.4 Exclusion Criteria

1. Any other central or peripheral nervous system disease that may interfere with the evaluation of ALS or its progression.
2. Presence of a tracheostomy, or use of permanent assistive ventilation (ventilatory support for 23 hours per day or more).
3. Previous exposure to AT-1501.
4. History of malignancy within the previous 5 years, except for localized non-melanoma skin cancers.
5. Women who are pregnant, expecting to get pregnant or who are breast feeding.
6. Abnormal function of the immune system resulting from:
  - Clinical conditions affecting the immune system (e.g. HIV infection, agammaglobulinemia),
  - Systemic administration of corticosteroids (PO/IV/IM) at a dose equivalent to 20 mg/day of prednisone for more than 14 consecutive days within 90 days prior to screening,

- Administration of anti-neoplastic and/or immunomodulating agents (e.g. TNF  $\alpha$  antagonists or anti-B cell antibodies) or radiotherapy within 1 year prior to screening.
7. Recipient of Stem Cell or Gene Therapy.
  8. Serum AST or ALT value greater than 3 times the ULN.
  9. Serum creatinine value greater than 1.5 times the ULN.
  10. Positive test for Hepatitis B surface antigen, Hepatitis C antibody, or HIV.
  11. History of deep venous thrombosis or pulmonary embolism.
  12. Exposure to any other experimental or investigational agent within 30 days or 5 half-lives; whichever is longer.
  13. History of active substance abuse within the past 2 years;
  14. History of stroke, poorly controlled or significant cardiovascular disease, diabetes or any other acute or chronic medical condition that would unreasonably increase the risks of the study procedures, as determined from an interview with the participant and/or review of medical records.
  15. Any other medical condition such as COVID-19, medication, or pre-planned medical/surgical procedure that, in the opinion of the Investigator, would compromise the safety of patients or the integrity of study results.

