11.2 Prior and Concomitant Medications

Prior and concomitant medications will be coded using World Health Organization Drug Dictionary (WHODrug) Global (B3, March 2020) and summarized to the therapeutic drug class (Anatomical

Therapeutic Chemical [ATC] 4 classification) and preferred name. If the ATC 4 classification is not provided, the next highest classification that is provided in the coding dictionary will be used. The preferred name will be defined as the active ingredient; if the active ingredient is not provided or includes more than two ingredients (e.g., multivitamins), then the drug name will be summarized as the preferred name.

Prior medications are those medications taken before the date of the first dose of study drug. Concomitant medications are defined as those medications listed as having been taken (1) prior to initiation of study drug administration and continuing for any period of time following the first administration of study drug or (2) starting at any time following the first administration of study drug. For any medications with missing information such as unknown start and end dates and unclear status (if taken prior to the study, or if ongoing), the medications will be reported as concomitant medications. Concomitant medications will be summarized using the Safety Analysis Set. Medications will be tabulated for each dose group using discrete summary statistics. Subjects may have more than one medication per ATC class. At each level of subject summarization, a subject will be counted once if he/she reports one or more medications. Percentages will be based on the number of subjects in each dose group. In the summaries, ATC classes and preferred names within an ATC class are listed in alphabetical order.

A subject listing of prior and concomitant medication will be provided.

12. Treatment Exposure

Calculated dose (mg/kg) will be derived as described below and summarized along with total dose received (mg) by dose group and visit using continuous descriptive statistics and Safety Analysis Set. Counts and percentages for the number of doses administered will be summarized by dose group.

Calculated Dose (mg/kg) = Total Dose Received (mg) / Weight (kg),

where weight is the weight at Screening. If there is a weight change of 10% or greater from the weight at Screening to a dosing visit, the weight at the dosing visit will be used.

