13.1 Adverse Events

An AE is any untoward medical occurrence in a subject or clinical investigation subject administered a pharmaceutical product (which does not necessarily have a causal relationship with this treatment) reported during or after having received the investigational drug/procedure. An AE can therefore be any unfavorable and unintended sign (including an abnormal laboratory finding), symptom, or disease

temporally associated with the use of an investigational product (IP), whether or not related to the IP. Treatment-emergent adverse events (TEAEs) are defined as any event that occurs or worsens on or after the first dose of study medication. All TEAEs will be collected from the first administration of IP until completion of the final visit.

A serious adverse event (SAE) is an AE that results in any of the following outcomes: death, life-threatening, persistent, or significant disability/incapacity, prompts a hospital admission or prolongs hospitalization, congenital anomaly/birth defect, or other important medical events. All SAEs will be collected from the time of informed consent until completion of the final visit.

All AEs will be evaluated by the Investigator/designee for duration, severity, seriousness, and relationship to investigational product. In addition, the actions taken for the AE will also be documented on the eCRF. Only symptoms that increase in severity or frequency after IP administration or new symptoms of illness will be recorded as AEs in the eCRF. If the event reflects worsening symptoms, then this should be captured in the event term. Untoward medical events which occur after signature of the informed consent but before IP administration will be recorded as medical history.

Serious adverse events recorded in the eCRF which began prior to the first dose of study medication will not be included in the summary tables but will be included in the AE data listings. AEs will be coded using MedDRA Version 23.1. Severity of AEs will be assessed as Grade 1 (lowest severity) to 5 (highest severity) using the National Cancer Institute Common Terminology Criteria for Adverse Events (NCI-CTCAE) Version 4.03. Relationship to study drug will be categorized as Not Related, Unlikely, Possible, Probable, and Related. Related AEs will be classified as those categorized as Probable, Possible, Related; or those missing an assessment of relationship to study drug.

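### Does reporting on-study procedures with medical history, with no split at first dose, blur what happened under AT-1501?

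*SAP*

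**What the plan says.** SAP 11.1 describes a summary of medical history by dose group, system organ class (SOC) and preferred term (PT), which is Table 14.1.3. It then adds that "On study procedures or surgeries will be coded using MedDRA 23.1 and reported with medical history". On output for procedures, it says that "A subject listing for medical history including procedure or surgeries will be provided" (Listing 16.2.4.4). The counting rule for the summary is "If a subject reports the same PT multiple times within the same SOC, that PT will only be reported once within that SOC".

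The SAP does not define *on study*. Protocol 6.2 says "Once the consent form is signed the participant is considered enrolled into the study", so the term can be read as running from consent through dosing to the last visit.

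First dose is the dividing line elsewhere in the SAP:

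- Section 11.2: "Prior medications are those medications taken before the date of the first dose of study drug".
- Section 13.1: "Treatment-emergent adverse events (TEAEs) are defined as any event that occurs or worsens on or after the first dose of study medication".
- Section 13.1: "Serious adverse events recorded in the eCRF which began prior to the first dose of study medication will not be included in the summary tables"; the same sentence then sends those events to the adverse event listings.

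The visible SAP indexes contain no separate table or listing for procedures.

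**The concern.** Medical history normally means the participant's state before treatment. Protocol 8.1.1 collects it to judge eligibility, the schedule of events places it at Screening, and both documents assign untoward events between consent and first dose to history. Sending on-study procedures to the same place with no date filter seems to cross that line.

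Such procedures can occur. Exclusion 15 bars only a "pre-planned medical/surgical procedure that, in the opinion of the Investigator, would compromise the safety of patients" or the integrity of the results, so other planned procedures remain possible, as do unplanned ones.

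If post-dose procedures were counted in Table 14.1.3, a row could mix history with on-treatment surgery. A procedure whose PT the participant already had would vanish under the once-per-PT rule. In a trial whose primary objective is safety, a reader would want to know which procedures took place under AT-1501.

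**Working it through.** The documents state no figure to reproduce. The check is mainly one of text, with a short bound on size.

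**1. Which output is established?** SAP 11.1 names procedures explicitly for the listing only. The SOC/PT summary is described for medical history, and Table 14.1.3 is titled simply as medical history. To be reported *with* history may or may not mean counted in that table. The listing is therefore certain and the table is open.

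**2. Does a combined listing break the SAP's own convention?** No. Prior and concomitant medications share one listing (16.2.4.5). Serious events that began before first dose are kept out of the tables but appear in the adverse event listings. Putting pre-dose and post-dose records in one listing is this SAP's usual practice. The first-dose rules in 11.2 and 13.1 cover medications and adverse events; none is written for procedures.

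**3. Where does a post-dose procedure surface?**

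| Situation after first dose | Where it is reported |
|---|---|
| An untoward condition leads to the procedure | Adverse event, counted as treatment-emergent by dose group (SAP 13.1) |
| That condition prompts hospital admission or is an important medical event | Also a serious adverse event (Protocol 10.2.1, SAP 13.1) |
| The procedure causes a complication | Adverse event, treatment-emergent |
| Planned procedure, nothing untoward | Medical history listing; possibly Table 14.1.3 |

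Only the last row lacks a safety output. A procedure with nothing untoward is not an adverse event under Protocol 10.1. The primary endpoint (Protocol 5.2.1, SAP 2.2) does not include procedures, and Protocol 11.3.4 lists no procedure summary among the safety analyses.

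**4. Size under the less favourable reading.** Suppose procedures do enter Table 14.1.3. Planned cohort sizes are 9, 9, 18 and 18 (SAP 3.1). One participant with a PT not already in their history adds:

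- 1/9 = 11.1 percentage points at 1.0 or 2.0 mg/kg;
- 1/18 = 5.6 percentage points at 4.0 or 8.0 mg/kg;
- 0 if the PT is already in that participant's history.

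If one replacement per cohort is assumed, these become 1/10 = 10.0 and 1/19 = 5.3. Any single record has this effect in cohorts of this size, so the figures describe the denominators and not a bias. The documents give no expected number of procedures, so the number of affected rows cannot be estimated.

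**5. Calendar share.** With the longest screening (30 days) and end of study on Day 101, 101/(30 + 101) = 101/131 = 77% of the time since consent falls on or after first dose. That shows the rule can reach post-dose time. It does not show how many procedures occur or are misread, so it is not an effect size.

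**The case for a change.** The best case for a change is that it costs almost nothing: define the term, limit Table 14.1.3 to records starting before first dose, and mark later procedures. Without this, a programmer must choose a rule. Dates in a listing would not correct a summary table, and the SAP does not promise dates in that listing. SAP 11.2 even supplies a default for medications with unknown dates, and procedures have none.

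Much of this stands as description. There is no date rule, no definition and no separate output, and a sentence of clarification would be harmless. It does not stand that readers *cannot* tell history from on-treatment procedures. The listing layout is not in the documents, so the most that can be said is that the SAP does not state how the distinction will be shown. Nor does it stand that rows are inflated or procedures absorbed, because both depend on table inclusion, which the text leaves open. A separate output by dose group with linked adverse events goes beyond what the ambiguity needs and could be nearly empty.

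**Conclusion.** No change to the plan is called for. SAP 11.1 leaves a presentation detail unstated: what *on study* covers, and whether procedures enter Table 14.1.3 as well as Listing 16.2.4.4. The analyst can settle this when the table and listing layouts are drawn up, by comparing each procedure's date with first dose, assuming those dates are recorded.

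Followed as written, the plan still counts every recorded untoward event that starts or worsens after dosing, by dose group. The worst visible effect is a descriptive history row shifted by 11.1 or 5.6 percentage points per affected participant, and only if procedures are counted in the table. No analysis in the visible text uses that table as an input. The conclusion assumes that sites record the condition behind a procedure, or any complication of it, as an adverse event, as Protocol 10.1.1 requires.

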11.2 Prior and Concomitant Medications

Prior and concomitant medications will be coded using World Health Organization Drug Dictionary (WHODrug) Global (B3, March 2020) and summarized to the therapeutic drug class (Anatomical

Therapeutic Chemical [ATC] 4 classification) and preferred name. If the ATC 4 classification is not provided, the next highest classification that is provided in the coding dictionary will be used. The preferred name will be defined as the active ingredient; if the active ingredient is not provided or includes more than two ingredients (e.g., multivitamins), then the drug name will be summarized as the preferred name.

Prior medications are those medications taken before the date of the first dose of study drug. Concomitant medications are defined as those medications listed as having been taken (1) prior to initiation of study drug administration and continuing for any period of time following the first administration of study drug or (2) starting at any time following the first administration of study drug. For any medications with missing information such as unknown start and end dates and unclear status (if taken prior to the study, or if ongoing), the medications will be reported as concomitant medications. Concomitant medications will be summarized using the Safety Analysis Set. Medications will be tabulated for each dose group using discrete summary statistics. Subjects may have more than one medication per ATC class. At each level of subject summarization, a subject will be counted once if he/she reports one or more medications. Percentages will be based on the number of subjects in each dose group. In the summaries, ATC classes and preferred names within an ATC class are listed in alphabetical order.

A subject listing of prior and concomitant medication will be provided.

12. Treatment Exposure

Calculated dose (mg/kg) will be derived as described below and summarized along with total dose received (mg) by dose group and visit using continuous descriptive statistics and Safety Analysis Set. Counts and percentages for the number of doses administered will be summarized by dose group.

Calculated Dose (mg/kg) = Total Dose Received (mg) / Weight (kg),

where weight is the weight at Screening. If there is a weight change of 10% or greater from the weight at Screening to a dosing visit, the weight at the dosing visit will be used.

A subject listing of the study drug dosing will be provided along with the subject weight at each dosing visit and calculated dose (mg/kg). A subject listing of the phone calls made following the dosing week will be provided as well.

13. Safety Analyses

All safety analyses will be conducted using the Safety Analysis set. Safety will be summarized by dose group.

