### Pre-Dose

- Review concomitant medications
- Symptom directed physical exam including weight
- Vital signs after 5 minutes in a supine or seated position (blood pressure, heart rate, temperature, respiration rate)
- Blood and urine samples for serum chemistry, CBC with differential and platelet count, coagulation tests, and urinalysis
- [REDACTED]
- Urine test for pregnancy
- [REDACTED]
- Administration of C-SSRS

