## 8 PROCEDURES AND EVALUATIONS

### 8.1 Assessments of Safety

#### 8.1.1 Medical History and Physical Examination

A medical history is obtained through review of the participant's medical records and personal interview in order to assess eligibility. Assessment of eligibility should include a full review of all concomitant medications and relevant vaccinations or immunizations.

A complete physical examination is performed at the screening visit as well as a COVID-19 test to be conducted no later than a week prior to the first infusion. The complete physical examination will include measurement of height, weight and vital signs. A symptom-directed physical examination (including examination of the injection site and weight) and vital signs is performed pre-dose on the days of dosing. Vital signs include heart rate, respiratory rate, blood pressure (after being seated/supine for at least 5 minutes) and temperature.

A weight change of 10% or greater from the previous measurement will warrant a recalculation of the AT-1501 dose.

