**Appendix A Schedule of Events**

	Screening	Dosing			Telephone Check	Dosing	Follow-up
Visit	1	2			3, 5, 7, 9, 11, 13	4, 6, 8, 10, 12	14
Study Week	Weeks -4 to -1	Week 1			Weeks 2, 4, 6, 8, 10 and 12	Weeks 3, 5, 7, 9 and 11	Week 15
Study Day	Day -30 to -1	Day 1 Pre-dose	Day 1 Dose	Day 1 Post-dose	Days 8, 22, 36, 50, 64, 78 (+/-2 days)	Days 15, 29, 43, 57, 71 (+/-2 days)	Day 101 (+/-7days)
Informed Consent	X						
Medical History and Demographics	X						
Record Concomitant Medications	X	X	X	X	X	X	X
Review Eligibility Criteria	X	X					
Physical Examination 	X	X				X	X
Vital Signs 	X	X	X	X		X	X
Weight 	X					X	
Height	X						
ECG 	X			X 		X 	X
COVID-19 testing 	X						
Blood/Urine Samples for Eligibility/Safety Testing 	X 	X 				X 	X 
████████████████████		■				██████████	■
████████████████████		■		■		██████████	■
████████████████████	■	■				██████████	■
████████	■	■				██████████	■
████████	■	■				██████████	■
Colombia Suicide Severity Rating Scale	X	X				X (pre-dose)	X
AT-1501 1-hr Infusion 			X			X	
Report Serious Adverse Events only	X	X					
Assess for All Adverse Events			X	X	X	X	X

- 1 Complete physical examination at Screening; symptom-directed physical examination at other times.
- 2 Vital signs (blood pressure, heart rate, temperature, respiration rate) are taken after being seated/supine for 5 minutes at Screening and then pre-dose, 15 minutes into the infusion and 1 and 2 hours post-infusion. Assessments performed post-infusion are timed from the end of the 1-hour infusion, not the IV-line flush. Vital signs may be collected within  $\pm 5$  min of the 15 minute timepoint and  $\pm 15$  min of the 1 and 2 hour post-infusion timepoints.
- 3 Weight for dose calculation is taken at Screening and on each dosing day pre-infusion. A weight change of 10% or greater will warrant a recalculation of the AT-1501 dose.
- 4 Post-infusion ECGs should be read on the day they are taken before the participant is released.
- 5 Eligibility testing includes serum chemistry, CBC with differential and platelet count, coagulation tests, serum pregnancy, HIV, HBC, HCV and urinalysis
- 6 Safety testing includes serum chemistry, CBC with differential and platelet count, coagulation tests, urinalysis and urine pregnancy test
- 7 Blood samples for safety testing pre-dose on dosing days only.

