8.2 Derivation of Screening Visit

Subjects may be rescreened when failing initial screening or falling out of the screening window. To incorporate the results from the rescreening visit, screening will be derived as the last visit before the dosing visit on Day 1, inclusive of unscheduled assessments. This screening result will be reported in summary tables, demographic, and study drug dosing listings.

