Appendix: Schedule of Events

	Screening	Dosing			Telephone Check	Dosing	Follow-up
Visit	1	2			3, 5, 7, 9, 11, 13	4, 6, 8, 10, 12	14
Study Week	Weeks -4 to -1	Week 1			Weeks 2, 4, 6, 8, 10 and 12	Weeks 3, 5, 7, 9 and 11	Week 15
Study Day	Day -30 to -1	Day 1 Pre-dose	Day 1 Dose	Day 1 Post-dose	Days 8, 22, 36, 50, 64, 78 (+/-2 days)	Days 15, 29, 43, 57, 71 (+/-2 days)	Day 101 (+/-7days)
Informed Consent	X						
Medical History and Demographics	X						
Record Concomitant Medications	X	X	X	X	X	X	X
Review Eligibility Criteria	X	X					
Physical Examination ¹	X	X				X	X
Vital Signs ²	X	X	X	X		X	X
Weight ³	X					X	
Height	X						
ECG ⁴	X			X ⁴		X ⁴	X
COVID-19 testing ¹⁴	X						
Blood/Urine Samples for Eligibility/Safety Testing ^{5,6,7}	X ⁵	X ^{6,7}				X ^{6,7}	X ⁶
Spirometry ¹²	X	X				Weeks 5, 9, 11 (pre-dose)	X
Colombia Suicide Severity Rating Scale	X	X				X (pre-dose)	X
AT-1501 1-hr Infusion ¹³			X			X	
Report Serious Adverse Events only	X	X					
Assess for All Adverse Events			X	X	X	X	X

- 1 Complete physical examination at Screening; symptom-directed physical examination at other times.
- 2 Vital signs (blood pressure, heart rate, temperature, respiration rate) are taken after being seated/supine for 5 minutes at Screening and then pre-dose, 15 minutes into the infusion and 1 and 2 hours post-infusion. Assessments performed post-infusion are timed from the end of the 1-hour infusion, not the IV-line flush. Vital signs may be collected within +5 min of the 15-minute timepoint and +15 min of the 1- and 2-hour post-infusion timepoints.
- 3 Weight for dose calculation is taken at Screening and on each dosing day pre-infusion. A weight change of 10% or greater will warrant a recalculation of the AT-1501 dose.
- 4 Post-infusion ECGs should be read on the day they are taken before the participant is released.
- 5 Eligibility testing includes serum chemistry, CBC with differential and platelet count, coagulation tests, serum pregnancy, HIV, HBC, HCV, and urinalysis
- 6 Safety testing includes serum chemistry, CBC with differential and platelet count, coagulation tests, urinalysis, and urine pregnancy test
- 7 Blood samples for safety testing pre-dose on dosing days only.

- 13 AT-1501 to be infused over 1 hour using an IV pump. Assessments performed post-infusion are timed from the end of the 1-hour infusion, not the IV-line flush.

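### SAP 12 and protocol 8.1.1 use different reference weights for the 10% change, so the SAP's calculated mg/kg can depart from mg per weight used for dosing

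*SAP*

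**What the plan says.** SAP 12 derives a calculated dose as mg received over body weight and summarises it by dose group and visit. The default weight is Screening. The exception reads "If there is a weight change of 10% or greater from the weight at Screening to a dosing visit", in which case that visit's weight is used. Under SAP 8.2, "screening will be derived as the last visit before the dosing visit on Day 1, inclusive of unscheduled assessments", so the default denominator predates the first infusion. The results go to Table 14.1.5 and Listing 16.2.5.1; for the listing, SAP 12 says "A subject listing of the study drug dosing will be provided along with the subject weight at each dosing visit".

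Protocol 8.1.1 sets the dosing trigger: "A weight change of 10% or greater from the previous measurement will warrant a recalculation of the AT-1501 dose". Footnote 3 of protocol Appendix A says "Weight for dose calculation is taken at Screening and on each dosing day pre-infusion". It then gives the trigger with no reference weight, and the SAP appendix repeats it: "A weight change of 10% or greater will warrant a recalculation of the AT-1501 dose".

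**The concern.** Two rules share a 10% threshold but measure it from different weights. The protocol rule determines how many mg are prepared. The SAP rule determines the weight those mg are divided by. If they move at different times, the reported mg/kg compares a dose prepared on one weight with another weight.

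The protocol's reference also has two readings: the weight at the last visit, or the weight last used for dosing. SAP 12 returns mg per dosing weight in general only if sites dose on Screening weight whenever the visit weight is within 10% of it, and on the visit weight otherwise. The protocol does not state that rule.

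At stake is the visible by-visit mg/kg exposure summary in a study whose cohorts are defined in mg/kg. A reader could see an apparent under- or over-dose that did not occur.

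**Working it through.** The documents state no exposure figure to reproduce.

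**Inputs from the documents:** 8 mg/kg as the nominal dose; infusions on Day 1 and at Weeks 3, 5, 7, 9 and 11; the two 10% rules above; 18 participants in the 8 mg/kg cohort.

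**Assumptions:** every body weight below; Day 1 mg set from Screening weight; full infusion; no rounding of mg.

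**Formulas**
- mg given = 8 × dosing weight, with the dosing weight updated when the protocol trigger is met.
- SAP value = mg / Screening weight, or mg / visit weight if the visit weight is 10% or more from Screening.
- Hence SAP value / (mg per dosing weight) = dosing weight / SAP denominator. The two agree only when these weights are equal.

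**Check with constant weight.** At 80 kg throughout, mg = 640 and both measures give 640/80 = 8.00.

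**Case 1: loss, then partial regain.** 80 kg from Screening through Week 3, 71 kg at Week 5, 73 kg at Week 7.
- Week 5: (80 − 71)/80 = 11.25%. The dose is recalculated under both readings: 8 × 71 = 568 mg. The SAP also switches: 568/71 = 8.00.
- Week 7: (73 − 71)/71 = 2.8%, so no recalculation under either reading and mg stays at 568. Against Screening, (80 − 73)/80 = 8.75%, so the SAP returns to 80 kg: 568/80 = **7.10**, against 568/71 = **8.00** per dosing weight.
- If one of 18 follows this path and 17 are at 8.00, the Week 7 mean is (17 × 8.00 + 7.10)/18 = 7.95. The SD is √[(17 × 0.05² + 0.85²)/17] = 0.21 and the minimum 7.10, against 8.00, 0 and 8.00 per dosing weight.

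**Case 2: steady loss of 2% per interval, last-visit reading.** Six intervals: Screening to Day 1, then five to Week 11.
- No single change reaches 10%, so mg stays at 640.
- Week 11 weight = 80 × 0.98⁶ = 70.87 kg, which is 11.4% below Screening, so the SAP switches: 640/70.87 = **9.03**, against **8.00** per dosing weight. At Week 9 it reported 640/80 = 8.00, so the value jumps with no change in mg.
- The loss per interval that reaches 10% in six intervals is 1 − 0.9^(1/6) = 1.74%.
- If weight does not change between Screening and Day 1, five intervals at 2% give a 9.61% loss and the SAP still reports 8.00. Five intervals need 1 − 0.9^(1/5) = 2.09% each.
- Under the last-dosing-weight reading, the Week 11 dose is recalculated to 8 × 70.87 = 567 mg and both measures give 8.00.

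**Case 3: gain, then loss, last-visit reading.** 80, 85, then 76 kg.
- (85 − 76)/85 = 10.6%, so the dose is recalculated to 8 × 76 = 608 mg.
- (80 − 76)/80 = 5%, so the SAP keeps 80 kg: 608/80 = **7.60**, against **8.00** per dosing weight.

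Case 1 departs under both readings of protocol 8.1.1. Cases 2 and 3 depend on the last-visit reading.

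**The case against.** The strongest reply is that SAP 12 is an analysis derivation with one fixed, reproducible reference and need not mirror a dosing rule. Paths that separate the two may also be uncommon. Under the last-visit reading, Case 1 needs a 9 kg loss between consecutive visits and then some regain, in a disease the protocol introduction describes as progressive wasting. Even then the cohort mean moves only from 8.00 to 7.95. The Pharmacy Manual, which is not available here, may say which weight governs preparation, and the content of SAP 16 on changes from the protocol is not shown.

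Much of this stands as a limit on size. It does not remove the conflict: all three statements are complete sentences, and the SAP's precedence clause covers statistical methods only, so it cannot alter the mg prepared under the protocol.

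A reader might infer four stronger points, and the documents do not support them:
- *The row fails because it is not mg per same-day weight.* SAP 12 never promises that measure, and it can be recovered from the listed mg and visit weights.
- *The row is faulty because it mixes Screening and visit weights, or hides spread.* A row based on dosing weight would also mix initial and recalculated weights, and would return the nominal dose for every correctly prepared, fully infused dose.
- *The reported SD would be zero while all weights stay within 10% of Screening.* That requires every dose to be set from Screening weight and fully infused, and the documents establish neither.
- *Day 1 weights will be missing because the schedule's Weight row has no Day 1 mark.* Footnote 3 calls for a weight on every dosing day, protocol 7.2 lists "Symptom directed physical exam including weight" before the first dose, and protocol 8.1.1 says "A symptom-directed physical examination (including examination of the injection site and weight) and vital signs is performed pre-dose on the days of dosing". The missing mark is editorial.

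**Conclusion.** The point holds, at low severity. As written, the protocol and SAP rules can give a calculated mg/kg that is not mg per weight used for dosing. In the worked cases the reported values are 7.10, 7.60 and 9.03 against 8.00. These rest on assumed weights, on Day 1 mg set from Screening weight, and, for the last two, on the last-visit reading of protocol 8.1.1. With stable weight the measures agree under these assumptions.

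The documents give no weight-change data, so neither frequency nor typical size can be stated. The visible effect is confined to the mg/kg rows of Table 14.1.5, which is not marked for topline, and one column of Listing 16.2.5.1. SAP 13 summarises safety by dose group, so no visible adverse event, laboratory, vital sign or ECG summary changes.

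**What to change.** 1. In SAP 12, define the denominator as the weight actually used to prepare each dose. First check that this weight is recorded; the visible documents do not say.
2. Reconcile SAP 12, protocol 8.1.1 and footnote 3 in both schedules on the reference for the 10% change. No view is taken here on which dosing rule is right.

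Optional, as an enhancement and not an error correction: add a by-visit row of mg received divided by that visit's pre-infusion weight, left missing when the weight is absent, in line with the observed-data rule in SAP 8.1.

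Editorial: align the Weight row of both schedules with protocol 7.2 and footnote 3 for Day 1.

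The cost is one or two derivation lines and the check that the dosing weight is captured. The optional row adds one line to Table 14.1.5 and uses weights already due to be listed.
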